After the primary analysis, double-blind treatment period is maintained to Day 360, although sponsor members (except for blinded monitors) will be unblinded for the planned regulatory submission in Japan. Details are mentioned in [Section 6.4](#).

Figure 3-1 Study design

Placebo volume will be matched to test product volume within each dose and injection. For example, the placebo group for the 200 mg dose will receive 1.0 mL of placebo whereas the placebo group for the 300 mg dose will receive 1.5 mL of placebo. Study treatment will be administered by the unblinded investigator or nurse to blind the arm and dose strengths. Details are described in [Section 6.4](#). Each participant will receive a total of three injections of inclisiran or placebo ([Table 3-1](#)).

Table 3-1 Dosing regimens

Study Drug and Dose	Number of randomized participants	Volume (mL)
Placebo for 100 mg	12	0.5
100 mg inclisiran sodium	54	0.5
Placebo for 200 mg	21	1.0
200 mg inclisiran sodium	100	1.0
Placebo for 300 mg	21	1.5

Study Drug and Dose	Number of randomized participants	Volume (mL)
300 mg inclisiran sodium	100	1.5

After the first study drug administration, participants will be observed in the clinic for at least 4 hours to have vital signs completed before being discharged. Participants will receive a second dose of study drug at the Day 90 visit and a third dose at Day 270. Participants will be observed for 30 min after the second dose (Day 90) and the third dose (Day 270) to have vital signs collected. Participants will also undergo the scheduled visit assessments as per the Assessment Schedule (Table 8-1)

4 Rationale

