6.5 Dose escalation and dose modification

Investigational study treatment dose adjustments are not permitted.

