6.5.1 Dose modifications

Study drug administration should be temporarily interrupted or permanently discontinued in participants with:

1. Intolerable AEs, or if the investigator believes that continuing dosing will be detrimental to the participant's mental or physical health. This includes severe or serious reactions at the injection site and any anaphylactic type reactions.
2. Liver laboratory values meeting the study drug interruption criteria listed in [Table 16-4](#) and [Table 16-5](#).
3. Unexplained creatine kinase (CK) values $>5 \times$ ULN confirmed by repeat test when the CK elevation is associated with muscle pain, muscle tenderness and/or muscle weakness, or new onset renal dysfunction.

Study treatment may be restarted at the discretion of the investigator, if the reason for discontinuation has resolved.

The dose interruptions must be recorded on an appropriate eCRF.

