Following appropriate causality assessments, as outlined above, the causality of the treatment is estimated as "probable" i.e. $>50\%$ likely, if it appears greater than all other possible causes of liver injury combined. The term "treatment-induced" indicates *probably caused* by the treatment, not by something else, and only such a case can be considered a DILI case and should be reported as an SAE.

All cases confirmed on repeat testing meeting the laboratory criteria defined above, with no other alternative cause for LFT abnormalities identified, should be considered as "medically significant," and thus, meet the definition of SAE and should be reported as SAE using the term "potential treatment-induced liver injury." All events should be followed up with the outcome clearly documented.

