9.1 Discontinuation and completion

9.1.1 Study treatment discontinuation and study discontinuation

Discontinuation of study treatment for a participant occurs when study treatment is stopped earlier than the protocol planned duration and can be initiated by either the participant or the investigator.

The investigator must discontinue study treatment for a given participant if, he/she believes that continuation would negatively impact the participant's well-being.

Study treatment must be discontinued under the following circumstances:

- Participant/guardian decision
- Pregnancy
- Use of prohibited treatment as per recommendations in the prohibited treatment section
- Any situation in which study participation might result in a safety risk to the participant
- Following emergency unblinding
- Any laboratory abnormalities that in the judgment of the investigator, prevents the participant from continuing participation in the study

If discontinuation of study treatment occurs, the investigator should make a reasonable effort to understand the primary reason for the participant's premature discontinuation of study treatment and record this information.

Participants who discontinue study treatment or who decide they do not wish to participate in the study further should NOT be considered withdrawn from the study UNLESS they withdraw their consent (see 'Withdrawal of Informed Consent' section). **Where possible, they should return for the assessments indicated** in the Assessment Schedule. If they fail to return for these assessments for unknown reasons, every effort (e.g. telephone, e-mail, letter) should be made to contact the participant/pre-designated contact as specified in the lost to follow-up section. This contact should preferably be done according to the study visit schedule.

If the participant cannot or is unwilling to attend any visit(s), the site staff should maintain regular telephone contact with the participant, or with a person pre-designated by the participant. This telephone contact should preferably be done according to the study visit schedule.

After study treatment discontinuation, at a minimum, in abbreviated visits, the following data should be collected at clinic visits or via telephone/email contact:

- New / concomitant treatments
- AE/ SAE

The investigator must also contact the IRT to register the participant's discontinuation from study treatment.

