10.2 Additional Safety Monitoring

10.2.1 Liver safety monitoring

To ensure participant safety and enhance reliability in determining the hepatotoxic potential of an investigational drug, a standardized process for identification, monitoring and evaluation of liver events has to be followed.

Please refer to [Table 16-3](#) in Appendix 2 for complete definitions of liver laboratory triggers.

Once a participant is exposed to study treatment, every liver event defined in [Table 16-3](#) should be followed up by the investigator or designated personnel at the trial site, as summarized below. Additional details on actions required in case of liver events are outlined in [Table 16-4](#). Repeat liver chemistry tests (i.e. ALT, AST, TBL, PT/INR, ALP and GGT) to confirm elevation.

- These liver chemistry repeats will be performed using the central laboratory. If results will not be available from the central laboratory, then the repeats can also be performed at a local laboratory to monitor the safety of the participant. If a liver event is subsequently reported, any local liver chemistry tests previously conducted that are associated with this event should have results recorded on the appropriate eCRF.
- If the initial elevation is confirmed, close observation of the participant will be initiated, including consideration of treatment interruption if deemed appropriate.
- Discontinuation of the investigational drug (refer to the Discontinuation of study treatment section), if appropriate
- Hospitalization of the participant if appropriate
- Causality assessment of the liver event
- Thorough follow-up of the liver event should include
 - These investigations can include based on investigator's discretion: serology tests, imaging and pathology assessments, hepatologist's consultancy; obtaining more detailed history of symptoms and prior or concurrent diseases, history of concomitant drug use, exclusion of underlying liver disease

All follow-up information and procedures performed must be recorded as appropriate in the eCRF.

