If normal at baseline: ALT or AST > 8 x ULN	Normal	None	
 Study drug can be restarted only if another etiology is identified and liver enzymes return to baseline.
ALT or AST increase with bilirubin increase:			
If normal at baseline: ALT or AST > 3 x ULN	TBL > 2 x ULN (or INR > 1.5)	None	
If elevated at baseline: ALT or AST > 2 x baseline or > 300 U/L (whichever occurs first)	For patients with Gilbert's syndrome: Doubling of direct bilirubin		
If normal at baseline: ALT or AST > 3 x ULN	Normal or elevated		

ALT or AST	TBL	Liver Symptoms	Action
If elevated at baseline: ALT or AST > 2 x baseline or > 300 U/L (whichever occurs first)		Severe fatigue, nausea, vomiting, right upper quadrant pain	

Table 16-5 Follow up requirements for liver laboratory triggers

[figure not shown]
Criteria	Actions required	Follow-up monitoring
Total Bilirubin (isolated)		
>1.5 – 3.0 ULN	
 Maintain treatment Repeat LFTs within 48-72 hours 	Monitor LFTs weekly until resolution ^a to ≤ Grade 1 or to baseline
> 3 - 10 × ULN (in the absence of known Gilbert syndrome)	
 Interrupt treatment Repeat LFT within 48-72 hours Hospitalize if clinically appropriate Establish causality Record the AE and contributing factors (e.g. conmeds, med hx, lab) in the appropriate CRF 	Monitor LFTs weekly until resolution ^a to ≤ Grade 1 or to baseline (ALT, AST, total bilirubin, Alb, PT/INR, ALP and GGT) Test for hemolysis (e.g. reticulocytes, haptoglobin, unconjugated [indirect] bilirubin)
> 10 x ULN	
 Discontinue the study treatment immediately Hospitalize the participant Establish causality Record the AE and contributing factors(e.g. conmeds, med hx, lab)in the appropriate CRF 	ALT, AST, total bilirubin, Alb, PT/INR, ALP and GGT until resolution ^c (frequency at investigator discretion)
Any AE potentially indicative of a liver toxicity*	
 Consider study treatment interruption or discontinuation Hospitalization if clinically appropriate Establish causality Record the AE and contributing factors(e.g., conmeds, med hx, lab)in the appropriate CRF 	Investigator discretion

^aResolution is defined as an outcome of one of the following: (1) return to baseline values, (2) stable values at three subsequent monitoring visits at least 2 weeks apart, (3) remain at elevated level after a maximum of 6 months, (4) liver transplantation, and (5) death.

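### Section 6.5.1 allows restart after a liver interruption at investigator discretion, where Table 16-4 would forbid it

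*Protocol*

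**What the plan says.** Section 6.5.1 gives three reasons to interrupt or permanently stop study drug: intolerable adverse events, liver values, and symptomatic or renal-associated CK elevation. The liver item reads "Liver laboratory values meeting the study drug interruption criteria listed in" Tables 16-4 and 16-5. One sentence on restarting follows the list and covers all three reasons without distinction: "Study treatment may be restarted at the discretion of the investigator, if the reason for discontinuation has resolved".

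Table 16-4 (Appendix 2, Section 16.2) sets the actions for transaminase-based liver triggers. Its interruption action calls for stopping the drug, repeat testing, close monitoring and a search for other causes, and then states: "Study drug can be restarted only if another etiology is identified and liver enzymes return to baseline". Table 16-5, for isolated bilirubin elevation, also has an interruption row but gives no restart condition.

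Three other sections touch on the matter:

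- Section 10.2.1, on liver monitoring: "Additional details on actions required in case of liver events are outlined in" Table 16-4.
- Section 9.1.1, among the reasons for mandatory discontinuation: "Any laboratory abnormalities that in the judgment of the investigator, prevents the participant from continuing participation in the study".
- Section 6.5.2.1, on confirmed cases of combined transaminase and bilirubin elevation: those "with no other alternative cause for LFT abnormalities identified, should be considered as" medically significant, and so reported as serious adverse events.

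**The concern.** The two restart rules differ in what they require. Section 6.5.1 asks only that the reason has resolved. Table 16-4 asks for an identified alternative cause and a return of enzymes to baseline, both together. Section 6.5.1 cites the table for when to stop, then supplies its own rule for when to resume, so it reads as a complete instruction.

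The difference falls in the worst place. A liver signal that clears with no explanation is the one where study drug remains a candidate cause, and Section 6.5.2.1 itself treats liver injury from the drug as a diagnosis reached by excluding other causes. Section 6.5 says "Investigational study treatment dose adjustments are not permitted", so a restart means re-exposure at the full assigned dose. Investigators who assess safety are blinded (Section 6.4), and an emergency code break requires permanent discontinuation (Section 6.6.3), so any decision to resume is made without knowing the arm. What is at stake is participant safety and consistent conduct across about 50 sites.

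**Working it through.** No statistical formula applies to the main point. The check is a comparison of the two rules, case by case, followed by a rough count of how often they could matter.

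**Comparison.** Take a participant interrupted under Table 16-4, for example with ALT above 8 x ULN.

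| State at the next dosing visit | Section 6.5.1 | Table 16-4 |
|---|---|---|
| Back to baseline, other cause found | Restart allowed | Restart allowed |
| Back to baseline, no cause found | Restart allowed | Restart barred |
| Improved but above baseline, other cause found | Depends on the meaning of resolved | Restart barred |
| Improved but above baseline, no cause found | Depends on the meaning of resolved | Restart barred |

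The second row is a clear difference. The third and fourth are arguable, because Section 6.5.1 does not define resolution. The footnote to Table 16-5 does define it for that table, and its definition includes values that have stabilised or stayed elevated. It does not formally govern Section 6.5.1, but it shows that resolution need not mean a return to baseline.

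**Search for a precedence rule.** Sections 6.5.1, 6.5.2.1, 9.1.1 and 10.2.1 and Tables 16-4 and 16-5 were read for one. Section 10.2.1 points to Table 16-4 for actions but does not place it above Section 6.5.1. Section 9.1.1 leaves stopping for laboratory findings to judgment. Section 6.5.2.1 has no restart rule. None states which text prevails.

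**Opportunities.** Section 3 says: "Participants will receive a second dose of study drug at the Day 90 visit and a third dose at Day 270". Each participant therefore has two re-dosing visits.

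- Planned re-dosing visits: 308 x 2 = 616 at most.
- Gaps between doses: 90 - 1 = 89 days and 270 - 90 = 180 days. Enzymes may well have settled by the next visit whatever the cause (an inference, not a statement in the protocol). The requirement for an identified cause is then the main safeguard.
- An interruption arising after the Day 270 dose raises no restart question, since no further dose is planned.

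**Frequency.** The documents give no rate of Table 16-4 interruptions. Assume 0.5% to 2%.

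- All arms: 308 x 0.005 = 1.5; 308 x 0.02 = 6.2.
- Inclisiran arms (100 + 100 + 54 = 254): 254 x 0.005 = 1.3; 254 x 0.02 = 5.1.

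These count every interruption. Those who recover with no cause found, or without full return to baseline, and who still have a dose to come are fewer and could be none.

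**The case against.** The strongest reply is that the two texts do not strictly contradict each other. Section 6.5.1 grants a permission and Table 16-4 imposes a restriction; a site that follows the restriction breaches neither. The documents also lead the reader to the table: the liver item in Section 6.5.1 names it, Section 10.2.1 sends the reader there for actions, and the restart condition sits in the same action text as the instruction to interrupt. This stands as far as it goes. It shows that a careful site would probably act correctly. It does not show that the protocol requires it to, because the table is cited in Section 6.5.1 only for its stopping criteria.

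A second reply is that other safeguards exist. Section 9.1.1 also obliges the investigator to stop treatment where continuing could endanger the participant. Combined transaminase and bilirubin cases with no other cause are serious adverse events reportable within 24 hours (Section 10.1.3), sponsor medical staff are available for advice, and an independent committee reviews safety data. These make an inappropriate restart less likely, above all in the gravest cases. They rest on judgment or act after the event, and none is a restart rule.

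Third, the layout of Table 16-4 is broken in the available text. The restart condition appears with the rows for more than 5 x ULN lasting over two weeks and more than 8 x ULN. The later interruption rows, with raised bilirubin or INR or with symptoms, show blank action cells. A merged cell is the likely explanation, but it is an inference. The mismatch is therefore certain for at least some interruption criteria and probable for the rest.

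Finally, Section 1.1 reports no increased hepatic risk with inclisiran in earlier studies, so events should be rare. That limits the size of the problem, not its existence.

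**Conclusion.** The concern holds. For a participant interrupted under Table 16-4 whose enzymes normalise without an identified cause, Section 6.5.1 permits a full-dose restart that the table forbids, and no text gives the order of precedence. The point does not extend to isolated bilirubin interruptions under Table 16-5, where there is no competing condition.

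The likely number affected is small: some fraction of roughly 2 to 6 interrupted participants out of 308, on an assumed interruption rate of 0.5% to 2% that the documents neither support nor refute. The sample size and primary analysis are untouched, because treatment discontinuation is handled by the treatment policy strategy (Protocol Section 2.1) and data collected afterwards are used (SAP Section 2.5.3). It should still be corrected, because the looser rule applies where the drug has not been ruled out and the repair costs almost nothing.

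**What to change.** Replace the restart sentence in Section 6.5.1 with wording such as: *After a temporary interruption, the investigator may resume study treatment once the reason for the interruption has resolved, except after a liver event meeting the interruption criteria of Table 16-4, for which the restart conditions in that table apply.*

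This also removes a smaller flaw. The present sentence speaks of resuming after discontinuation, which the glossary defines as a permanent stop; the new wording confines it to temporary interruption. When making the change, the sponsor should confirm that the restart condition in Table 16-4 is meant to cover every interruption row.

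The cost is one sentence, by minor amendment or clarification letter to sites. Visits, data collection and analysis do not change.

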6.5.2 Follow-up for toxicities

6.5.2.1 Follow up on potential drug-induced liver injury (DILI) cases

Participants with transaminase increase combined with total bilirubin increase may be indicative of potentially severe DILI, and should be considered as clinically important events and assessed appropriately to establish the diagnosis. The required clinical information, as detailed below, should be sought to obtain the medical diagnosis of the most likely cause of the observed laboratory abnormalities.

The threshold for potential DILI may depend on the participant's baseline AST/ALT and total bilirubin value; participants meeting any of the following criteria will require further follow-up as outlined below:

- For participants with normal ALT and AST and total bilirubin value at baseline: AST or ALT $> 3.0 \times$ ULN combined with total bilirubin $> 2.0 \times$ ULN
- For participants with elevated AST or ALT or total bilirubin value at baseline: [AST or ALT $> 2 \times$ baseline] OR [AST or ALT $> 300 \text{ U/L}$] whichever occurs first combined with [total bilirubin $> 2 \times$ baseline AND $> 2.0 \times$ ULN]

As DILI is essentially a diagnosis of exclusion, other causes of abnormal liver tests should be considered and their role clarified before DILI is assumed as the cause of liver injury.

A detailed history, including relevant information such as review of ethanol consumption, concomitant medications, herbal remedies, supplement consumption, history of any pre-existing liver conditions or risk factors, should be collected.

Laboratory tests should include ALT, AST, total bilirubin, direct and indirect bilirubin, gamma-glutamyl transferase (GGT), glutamate dehydrogenase (GLDH), prothrombin time (PT)/International Normalized Ratio (INR), alkaline phosphatase (ALP), albumin, and CK.

Perform relevant examinations (Ultrasound or Magnetic resonance imaging (MRI), Endoscopic retrograde cholangiopancreatography (ERCP)) as appropriate, to rule out an extrahepatic cause of cholestasis. Cholestasis (is defined as an ALP elevation $> 2.0 \times$ ULN with R value < 2 in participants without bone metastasis, or elevation of the liver-specific ALP isoenzyme in participants with bone metastasis).

Note: The R value is calculated by dividing the ALT by the ALP, using multiples of the ULN for both values. It denotes whether the relative pattern of ALT and/or ALP elevation is due to cholestatic ($R \leq 2$), hepatocellular ($R \geq 5$), or mixed ($R > 2$ and < 5) liver injury. For children, there are caveats to calculating the R-ratio as normal levels of ALP are higher than in adults with standard ranges varying by developmental age. In clinical situations where it is suspected that ALP elevations are from an extrahepatic source, the GGT can be used if available. GGT may be less specific than ALP as a marker of cholestatic injury, since GGT can also be elevated by enzyme induction or by ethanol consumption. It is more sensitive than ALP for detecting bile duct injury (<https://livertox.nih.gov/rucam.html>).

Table 6-4 provides guidance on specific clinical and diagnostic assessments which can be performed to rule out possible alternative causes of observed liver function test (LFT) abnormalities.

Table 6-4 Guidance on specific clinical and diagnostic assessments which can be performed to rule out possible alternative causes of observed LFT abnormalities

Disease	Assessment
Hepatitis A, B, C, E	
IgM anti-HAV; HBsAg, IgM & IgG anti-HBc, HBV DNA; anti-HCV, HCV RNA, IgM & IgG anti-HEV, HEV RNA
CMV, HSV, EBV infection	
IgM & IgG anti-CMV, IgM & IgG anti-HSV; IgM & IgG anti-EBV
Autoimmune hepatitis	
ANA & ASMA titers, total IgM, IgG, IgE, IgA
Alcoholic hepatitis	
Ethanol history, GGT, MCV, CD-transferrin
Nonalcoholic steatohepatitis	
Ultrasound or MRI
Hypoxic/ischemic hepatopathy	
Medical history: acute or chronic CHF, hypotension, hypoxia, hepatic venous occlusion. Ultrasound or MRI.
Biliary tract disease	
Ultrasound or MRI, ERCP as appropriate.
Wilson disease (if <40 yrs old)	
Ceruloplasmin
Hemochromatosis	
Ferritin, transferrin
Alpha-1-antitrypsin deficiency	
Alpha-1-antitrypsin

Other causes should also be considered based upon participants' medical history (hyperthyroidism / thyrotoxic hepatitis – T3, T4, TSH; CVD / ischemic hepatitis – ECG, prior hypotensive episodes; T1D / glycogenic hepatitis).

Following appropriate causality assessments, as outlined above, the causality of the treatment is estimated as "probable" i.e. $>50\%$ likely, if it appears greater than all other possible causes of liver injury combined. The term "treatment-induced" indicates *probably caused* by the treatment, not by something else, and only such a case can be considered a DILI case and should be reported as an SAE.

All cases confirmed on repeat testing meeting the laboratory criteria defined above, with no other alternative cause for LFT abnormalities identified, should be considered as "medically significant," and thus, meet the definition of SAE and should be reported as SAE using the term "potential treatment-induced liver injury." All events should be followed up with the outcome clearly documented.

